7.3.4	Protections to Minimize Risks with Spirometry	27
7.3.5	Protections to Minimize Risks with Measuring FMD	28
7.3.6	Protections to Minimize Risks with Measuring LVS	28
7.3.7	Protections to Minimize Risks with Other Study Procedures	28
7.3.8	Protections to Minimize Risks with Breach of Confidentiality	28
7.4	REPORTING OF AEs AND SAEs	29
7.5	INFORMED CONSENT	29
7.6	CONFIDENTIALITY	29
7.7	INVESTIGATORS, FACILITIES, AND INSTITUTIONAL REVIEW BOARD	29
8	REFERENCES	30

List of Abbreviations

5-NO₂-γT: 5-nitro-gamma tocopherol

γT: gamma tocopherol

γ-CEHC: 2,7,8-trimethyl-2-(B-carboxy-ethyl)-6-hydroxychroman

αT: alpha tocopherol

α-TTP: alpha tocopherol transfer protein

ANC: absolute neutrophil count

AUC: area under the curve

BAR: brachial artery reactivity

BSA: body surface area

COX-2: cyclooxygenase-2

CYP3A: cytochrome P450 3A

FA: filtered air

FMD: flow mediated dilation

FDR: fractional disappearance rate

FEF₂₅₋₇₅: forced expiratory flow during mid portion (25%-75%) of forced vital capacity

FEV₁: forced expiratory volume in 1 second

FRC: functional residual capacity

FVC: forced vital capacity

GSTM1: glutathione-S-transferase mu 1

HF: high frequency

HRV: heart rate variability

IDS: investigational drug service

LDMS: lab data management system

LF: low frequency

LPS: lipopolysaccharide

LVS: left ventricular strain

mT-γT: mixed tocopherol-γT

NSBR: nonspecific bronchial reactivity

O₃: ozone

PBMC: peripheral blood mononuclear cell

PC₂₀: provocative concentration resulting in 20% reduction in FEV₁

PF: peak flow

PGD₂/PGE₂: prostaglandin D₂/prostaglandin E₂

PM: particulate matter

PPM: parts per million

PMN: polymorphonuclear leukocytes

PNN50: mean number of times per hour in which the change in consecutive normal sinus (NN) intervals exceeds 50 milliseconds

QTVI: QT variability index

SDNN: standard deviation of normal to normal R-R intervals

TEOM: tapered element oscillating microbalance

T_{H1}: T helper type 1

VAPS: versatile air pollution sampler

VLF: very low frequency

WSP: wood smoke particles

Study Summary

Title	A phase II randomized, double blinded, placebo-controlled study of gamma tocopherol-enriched supplement on lower airway responses to inhaled wood smoke in healthy adults
Short Title	Gamma tocopherol for wood smoke-induced airway inflammation
IRB Number	17-2303
Phase	II
Study Duration	3 years
Study Center(s)	University of North Carolina Hospitals in Chapel Hill, North Carolina, 27599-7310
Objectives	To determine the efficacy of 1100 mg gamma tocopherol-enriched supplement for mitigating inhaled wood smoke particle-induced airway inflammation in healthy adults with no more than mild asthma
Number of Subjects	35 subjects

Diagnosis and Main Inclusion Criteria	Healthy adult volunteers with no more than mild asthma
Study Product, Dose, Route, Regimen	Gamma E Gems (J.R. Carlson Laboratories, Inc., [name] Arlington Heights, IL 60004.)
Statistical Methodology	Change in sputum % neutrophils (%PMNs) [Δ postWSP-preWSP (γ T) vs Δ postWSP-preWSP (placebo)]. Statistically significant differences will be determined using two-sample tests, either parametric (t-test) or non-parametric (Wilcoxon signed-rank test) depending on whether the normality assumption is met.

1. Introduction

This document is a protocol of a human research study. This study is to be conducted according to US and international standards for Good Clinical Practice (FDA Title 21 part 312 and International Conference on Harmonization guidelines), applicable government regulations and Institutional research policies and procedures.

1.1 Background

Asthma is among the most prevalent chronic diseases in the U.S. (1) and represents a source of significant burden to patients and healthcare systems. Acute exacerbation of asthma is characterized by airway inflammation, bronchoconstriction, increased production of airway mucus, and decreased mucociliary clearance with formation of mucus plugs (2, 3). While corticosteroids are often the treatment of choice, their use is associated with a number of adverse effects, particularly when administered systemically. Currently there is an unmet need for non-steroidal treatment options for asthma, and Vitamin E has been proposed as one such treatment to combat inflammatory features of asthma.

Among the isoforms of vitamin E that can be tested in asthma are α -tocopherol (α T), the predominant isoform found in over the counter Vitamin E supplements, and gamma tocopherol (γ T), the predominant isoform found in foods. Intervention trials of α T in humans with asthma have been generally disappointing (4, 5). However, γ T and its primary metabolite 2,7,8-trimethyl-2-(B-carboxy-ethyl)-6-hydroxychroman (γ -CEHC) have been shown to have a number of anti-inflammatory activities not observed with α T and its metabolites (6-10). These actions include scavenging reactive nitrogen species to form 5-nitro- γ -tocopherol (5-NO₂- γ T) (6) and inhibition of cyclooxygenase-2 (COX-2) and 5-lipoxygenase, reducing inflammatory eicosanoid production (7-9).

Particulate matter (PM) is a leading cause of respiratory tract and cardiovascular disease in the United States and world-wide. Wood smoke particles (WSP) derived from wildland and other fires account for a significant fraction of ambient air PM. Health effects associated with WSP include acute bronchitis, asthma exacerbation, pneumonia, cough and systemic inflammation. While these effects are seen in both healthy and asthmatic individuals, many studies indicate that asthmatics have increased susceptibility to the effects of WSP. Our center has developed a 500 μ g/m³ WSP exposure protocol (levels similar to those encountered by firefighters and residents

in close proximity to wildland burn sites) that induces airway and systemic inflammation in healthy volunteers. As with other pollutants, these inflammatory responses modulate non-specific bronchial reactivity (NSBR), inflammatory cell recruitment to the airways (primarily neutrophils), and potentially cardiovascular function.

Our team has focused on gamma tocopherol as a nutritional intervention to prevent inflammatory responses to air pollutants such as WSP. Building on animal and in vitro preclinical studies, we have established that 1400 mg/day of oral γ T-enriched supplement for 7 and 14 days in healthy volunteers and mild asthmatics, respectively, inhibited neutrophil influx into the airways, reduced production of sputum mucins, and improved mucociliary clearance following challenge with inhaled endotoxin, another common component of PM (10, 11). The findings occurred in the context of significantly increased plasma concentrations of γ T and its active metabolite γ -CEHC. Given our findings in these early phase clinical trials, γ T supplementation is an attractive approach to prevent WSP-induced adverse health effects. We propose to use γ T supplementation in a human model of WSP inhalation to mitigate key features of airway inflammation: inflammatory cell recruitment, production of inflammatory cytokines and mucous, and changes in airway physiology.

1.2. Investigational Agent

Gamma E Gems 548 mg softgels, (J.R. Carlson Laboratories, Inc., [name] Arlington Heights, IL 60004.)

1.3. Dose Rationale and Risk/Benefits

Gamma tocopherol will be administered in softgel form, with each softgel containing 874.1 mg of tocopherols, , including:

Alpha Tocopherol: 141.0 mg/sg (softgel)

Beta Tocopherol: 18.1 mg/sg

Gamma Tocopherol: 548.0 mg/sg

Delta Tocopherol: 167.0 mg/sg

Subjects will consume two softgels by mouth once daily for 7 days. This dosing regimen was chosen based on the results of our previous early phase clinical trials examining the impact of gamma tocopherol on LPS-induced airway inflammation in healthy adults (11) and adults with asthma (26). These studies tested a 7 and 14 day course of treatment, respectively, and found similar plasma concentrations of γ T and active metabolites in both studies. Furthermore, we showed in both studies that γ T significantly reduced LPS-induced sputum neutrophilia compared to placebo. Based on our previous findings, we will now study the efficacy of γ T for mitigating WSP-induced airway inflammation.

We have discussed the potential benefits of γ T supplementation for protection against ambient air pollutant-induced airway inflammation in healthy volunteers and adults with mild asthma in section 1.1. In terms of risk, the most significant safety concern for Vitamin E supplements in general is increased bleeding risk, and most trials have used supplements containing predominantly α T as opposed to γ T. The Alpha Tocopherol Beta Carotene cancer prevention

study, a randomized, double blind, placebo controlled trial of α T and β -carotene supplementation in middle aged male smokers, found that alpha tocopherol supplementation was associated with increased risk of fatal subarachnoid hemorrhage (13). To our knowledge, there are no published studies of γ T supplementation that show an increased risk of bleeding. In our own previous studies, we have not observed any significant bleeding events nor any changes in PT, aPTT, or INR with γ T supplementation at doses similar to the proposed study.

An additional area of concern was raised by findings from the Coronary Artery Risk Development in Young Adults (CARDIA) study, a population-based observational study. In this study, higher plasma γ T levels in young adults (not taking Vitamin E supplements) were associated with lower lung function measurements (FEV₁ and FVC) (14). However, others have shown that increased *dietary* vitamin E intake had protective effects on lung function in adults (15). Plasma γ T levels have not been significantly associated with risk of asthma or asthma outcomes. However, increased dietary vitamin E, which is predominantly gamma tocopherol (γ T), has been associated with decreased occurrence of asthma in both children (16-18) and adults (19).

Based on our own previous studies, the most common adverse effects of γ T are diarrhea, flatulence, abdominal bloating, and nausea. In our most recent randomized, placebo controlled crossover study evaluating 14 days of γ T-enriched supplementation (1400 mg daily) in 23 adult volunteers with asthma (26), diarrhea was reported in 6 participants (26%) on active treatment, compared to 1 participant (4.3%) on placebo. Nausea was reported in 6 participants (26%) on active treatment, compared to 2 participants (8.7%) on placebo. Bloating and flatulence were reported in 2 participants (8.7%) and 1 participant (4.3%) on active treatment, respectively, with no reports of these symptoms in subjects receiving placebo. One participant withdrew from the study due to intolerable gastrointestinal symptoms. In all other participants, gastrointestinal symptoms were transient in nature, beginning after the first or second dose of study drug and self-resolving despite continued treatment for the 14-day period.

2. Study Objective

The primary objective of this study is to examine the effectiveness of gamma tocopherol for mitigating inhaled WSP-induced airway inflammation in healthy adults and mild asthmatics, specifically airway inflammatory cell recruitment and cytokine production, mucous production, and non-specific bronchial reactivity.

3. Study Design

3.1. General Design

This study is designed to evaluate the effectiveness of gamma tocopherol for mitigating features of airway inflammation induced by inhaled WSP by examining airway inflammatory cell recruitment and cytokine production, and mucous production,. We anticipate 3 years will be required for completion of study visits for all participants.

Upon successful completion of two screening protocols (one as a general screen to determine eligibility for airway challenge studies and a second to identify those individuals who are deemed “responders” to WSP inhalation, defined as $\geq 10\%$ increase in sputum PMNs following exposure), participants will be enrolled to participate in a randomized, double blinded, placebo-controlled, crossover study consisting of 8 visits. Participants will be randomized to γ T or placebo treatment followed by chamber exposure with WSP. After a 4-week washout period, participants will cross over to the alternate treatment group.

Following randomization to placebo or gamma tocopherol treatment, subjects will return for baseline (V0) and training visits (V1). Participants will consume 1400 mg of γ T-enriched supplement or placebo once daily for 7 days. Participants will undergo WSP exposure (V2), then return the following day for a 24 hour post-exposure visit (V3). After a 4 week wash out period, subjects will present for a review of medical history and adverse events and cross over to the alternate treatment (V4). They will undergo a second WSP exposure (V5) followed by a 24 hour post-exposure visit (V6). Five to 10 days after the exposure, participants will return for a study completion visit (V7).

3.2. Primary Study Endpoint

The primary endpoint will be change in sputum %PMNs [Δ (postWSP (4 hr) – preWSP)[γ T] vs Δ (postWSP (4 hr) – preWSP)[placebo]] and change in sputum %PMNs [Δ (postWSP (24 hr) – preWSP)[γ T] vs Δ (postWSP (24 hr) – preWSP)[placebo]].

3.3. Secondary Study Endpoints

The secondary endpoints of the study will be change in peripheral blood absolute neutrophil count (ANC) in cells $\times 10^9/L$ [Δ (postWSP (4 hr) – preWSP)[γ T] vs Δ (postWSP (4 hr) – preWSP)[placebo]] and [Δ (postWSP (24 hr) – preWSP)[γ T] vs Δ (postWSP (24 hr) – preWSP)[placebo]].

Exploratory endpoints of interest include:

1. Role of asthma as a modifier of γ T treatment effect on WSP-induced airway inflammation
2. Spirometry measurements – forced vital capacity (FVC), forced expiratory volume in 1 second (FEV₁), FEV₁/FVC ratio
3. Secretion of sputum mucins (total sputum mucins, MUC5AC, MUC5B) will be determined by Western blot
4. Serum cytokine concentrations via Mesoscale:
 - a. TH1 cytokines: IL-1b, IL-6, IL-8, TNFa
5. Sputum cytokine concentrations via Mesoscale:
 - a. TH1 cytokines: IL-1b, IL-6, IL-8, TNFa
6. Flow mediated dilation (FMD) using brachial artery ultrasound
7. Left ventricular strain (LVS)
8. Serum concentrations of gT aT gCEHC and aCEHC.

3.4. Primary Safety Endpoints

Safety Endpoints: Safety endpoints include respiratory symptoms such as wheezing or shortness of breath requiring albuterol, significant bleeding events, or significant change in blood coagulation markers (PT, aPTT) such that these measurements are outside of normal range, and adverse events (AEs) and severe adverse events (SAEs). Exploratory safety endpoints include GI symptoms with γ T vs Placebo. Adverse event data will be collected through 7 days post study drug treatment for both treatment periods. UNC Chapel Hill Human Research Protection Program Standard Operating Procedures will be followed for reporting adverse events/unanticipated problems to the Biomedical IRB. All SAEs will be reported to the CDER of the FDA as well as to the UNC Biomedical IRB within 24 hours of recognition of the event. Adverse events will be reported to both the FDA and UNC IRB on no less than an annual basis, or when the protocol is completed.

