- f. Unwillingness to use if sexually active (IUD, implant, sterilization, or when used in combination: birth control pills/patch and barrier methods). (i.e., those that, alone or in combination, result in a failure rate of <1% per year when used consistently and correctly). Note that male condom use, hormonal contraceptive pills, or hormonal contraceptive patches used alone have estimated failure rates that do not meet these criteria.
- g. Abnormal PT or aPTT values at screening or during the treatment period. Normal values will be those published by the clinical lab (Labcorp, INC).
- h. Use of immunosuppressive or anticoagulant medications including routine use of NSAIDS. Oral contraceptives are acceptable, as are Antidepressants and other medications may be permitted if, in the opinion of the investigator, the medication will not interfere with the study procedures or compromise safety and if the dosage has been stable for 1 month.
- i. Orthopedic injuries or impediments that would preclude bicycle or treadmill exercise.
- j. Inability to avoid NSAIDS, Multivitamins, Vitamin C or E or herbal supplements.
- k. Allergy/sensitivity to study drugs or their formulations
- l. Known hypersensitivity to methacholine or to other parasympathomimetic agents

- m. Unwillingness to avoid coffee, tea, cola drinks, chocolate, or other foods containing caffeine after midnight on the days that methacholine challenge testing is to be performed.
- n. Positive test for Covid 19 in the past 90 days

2. Pregnant/nursing women and children (< 18 years as this is age of majority in North Carolina) will also be excluded since the risks associated with woodsmoke exposure to the fetus or child, respectively, are unknown and cannot be justified for this non-therapeutic protocol. Individuals over 45 years of age will not be included due to the increased possibility of co-morbidities and need for prohibited medications.
3. Inability or unwillingness of a participant to give written informed consent.

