5.1.6. Visits 3 (Period 1) and 6 (Period 2): 24 hours post-exposure

1. Review any adverse events
2. Vital signs, resting blood pressure, oxygen saturation
3. WSP Exposure symptom questionnaire
4. Venipuncture (CBC with differential, serum cytokines, serum C-reactive peptide, lipid panel, LDH, fibrinogen, PT, aPTT, INR, gT and metabolite levels)
5. Spirometry
6. Sputum induction
7. .

At least a 4 week, but no more than an 8 week washout is required between Period 1 and Period 2.

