6.2. Statistical Methods

Our analytic plan was developed in collaboration with [name], the biostatistician for the CEMALB, who will oversee all statistical analysis. For analysis of sputum and circulating PMN responses as well as cytokine changes within each treatment group, we will use (i) descriptive analysis, (ii) two-sample comparison test, and (iii) random effects regression analysis (Equation 1) designed to take advantage of the crossover design (22). Specifically, we will use the tabular and graphic methods to describe/explore the basic relationship between the groups. We will then follow up by comparing the Δ sputum %PMNs (post WSP – pre WSP [γ T]) vs (post WSP – pre WSP [placebo]) using two-sample tests, either parametric (T-Test) or nonparametric (Wilcoxon signed-rank test), depending on whether the normality assumption is met. We will transform the data to achieve normality if needed. Finally, we will employ a random effect regression modeling technique (Equation 1) that allows us to assess treatment effect while accounting for potential period effect and carry-over effects. This approach is similar to those we have previously described to assess genotype effects (including the GSTM1 null genotype) on response to pollutants (11, 23-25) and is shown below. In all analyses, criterion for significance will be $p \leq 0.05$. To address potential missing data, we will employ multiple imputation methods to address this issue when appropriate; using techniques we have previously described (24).

Linear mixed model approach for global unified analysis of data for secondary and exploratory outcomes:

$$Y_{11k} = \mu + \pi_1 + \tau_1 + \beta X_k + s_{1k} + \epsilon_{11k}; Y_{12k} = \mu + \pi_2 + \tau_2 + \lambda_1 + \beta X_k + s_{1k} + \epsilon_{12k}$$

$$Y_{21k} = \mu + \pi_1 + \tau_2 + \beta X_k + s_{2k} + \epsilon_{21k}; Y_{22k} = \mu + \pi_2 + \tau_1 + \lambda_2 + \beta X_k + s_{2k} + \epsilon_{22k}$$

μ is the grand mean, π_1 and π_2 are period effects, τ_1 and τ_2 are treatment effects, λ_1 and λ_2 are carryover effects for different sequences, s_{1k} and s_{2k} are individual random effects within each sequence, and ϵ 's are random errors. Subscript k is for subjects.

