7.3. Measures to Minimize Risk

7.3.1. Protections to Minimize Risk of Gamma Tocopherol

Tocopherols may affect coagulation. We will query volunteers for bruising and bleeding prior to enrollment and during the dosing period, and will monitor PT and aPTT values prior to the first dose of study drug and at the end of the dosing period. They may be checked at any time the subjects experiences abnormal bruising. Any participant with an abnormal baseline PT, aPTT or INR will be excluded from receipt of study treatment. Spirometry is performed at regular intervals throughout the γ T dosing period to monitor for any changes in lung function. As to the incidence of gastrointestinal symptoms, we will recommend that γ T supplements be taken with a high-fat meal to promote intestinal absorption of γ T and mitigate many associated diarrhea or bloating. Participants will receive a GI symptom diary to be completed daily while taking the study drug and returned to study coordinators on the morning of the challenge visits (Visit 2 or 5). All female subjects, except those who have had a hysterectomy with oophorectomy, will undergo urine pregnancy testing prior to beginning treatment and prior to WSP exposure. A positive pregnancy test will exclude the subject, and they will be withdrawn if they become pregnant during the course of the study. Study medication, including placebo, will be dispensed by the Investigational Drug Service of UNC Hospitals.

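### PT and aPTT are judged only by whether they leave the normal range, and no gamma tocopherol versus placebo comparison is planned, although V3 and V6 supply one

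*Combined protocol and SAP*

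**What the plan says.** Section 1.3 states that "the most significant safety concern for Vitamin E supplements in general is increased bleeding risk". It adds that most of the relevant trials used mainly alpha tocopherol, that the authors know of no published gamma tocopherol study showing more bleeding, and that their own studies saw no change in PT, aPTT or INR. Section 7.2.1 accepts that gamma tocopherol could share the risk but says this has not been shown.

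Section 3.4 lists, among the safety endpoints, a "significant change in blood coagulation markers (PT, aPTT) such that these measurements are outside of normal range". The limits are the laboratory's: "Normal values will be those published by the clinical lab" (4.2). An exclusion item in 4.2 reads "Abnormal PT or aPTT values at screening or during the treatment period", and 7.3.1 bars anyone with an abnormal baseline PT, aPTT or INR from study treatment.

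Section 7.3.1 says the team "will monitor PT and aPTT values prior to the first dose of study drug and at the end of the dosing period". In the visit lists (5.1.2 to 5.1.7) the draws fall at V0 and, under 5.1.6, at V3 and V6, where the blood panel includes "LDH, fibrinogen, PT, aPTT, INR, gT and metabolite levels". V1, V2, V4 and V5 have no PT or aPTT.

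Section 6.2 directs its comparisons at sputum and circulating neutrophils and at cytokines. Its model is introduced as a "Linear mixed model approach for global unified analysis of data for secondary and exploratory outcomes". Section 3.3 lists those outcomes, and PT, aPTT and INR are not among them. Section 3.4.2 asks only that significant abnormalities be assessed and reported. By contrast, 3.4 does name a between-treatment comparison for gastrointestinal symptoms.

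**The concern.** A laboratory range is wide relative to the change a mild drug effect would produce. If everyone starts inside it, a small prolongation shared by most participants moves few of them across the upper limit. Occasional out-of-range values also occur on placebo, and a count with no planned comparison gives no basis for attributing them.

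Both V3 and V6 follow wood smoke exposure by a day, so a change from V0 mixes drug and smoke. Only the active-minus-placebo contrast separates the two. The trial will hold the data for it but has no plan to use them. A null finding would then be a short list of abnormal values, when the same blood could give an estimate with an interval that bounds the effect.

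**Working it through.** **The plan's own figure.** The documents give no calculation for coagulation. Their only sample size is 28 (6.1), from an effect of 14.5 with SD 25.9. As a paired t-test, two-sided 0.05: noncentrality = (14.5/25.9) × √28 = 2.96, power 81.5%. The stated 28 is reproduced, as a number of within-person pairs.

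**Assumptions for coagulation.** None of these is in the documents:
- each marker is normal with between-person SD 1, and the range is mean ± 1.96 SD
- V0 is in range (this reflects 4.2 and 7.3.1)
- within-person correlation r is 0.5 to 0.8
- the active-versus-placebo count is tested by exact two-sided McNemar
- where PT and aPTT are combined, their mutual correlation is 0.3

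**Paired comparison.** SD of the difference = √(2(1 − r)), and noncentrality = shift × √28 / √(2(1 − r)). For a shift of 0.5:
- r = 0.5: SD 1.000, noncentrality 2.65, power 72%
- r = 0.7: SD 0.775, noncentrality 3.42, power 91%
- r = 0.8: SD 0.632, noncentrality 4.18, power 98%

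The 95% CI half-width is 2.052 × √(2(1 − r)) / √28. That is 0.39 SD at r = 0.5 and 0.25 SD at r = 0.8, so a null result would carry a usable bound.

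**Out-of-range count.** Simulated, 20,000 trials per setting, shift 0.5:

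| r | Out of range of 28, active vs placebo (one marker) | Power, one marker | Power, PT or aPTT |
|---|---|---|---|
| 0.5 | 2.0 vs 1.2 | 0.4% | 2.2% |
| 0.7 | 1.8 vs 1.0 | 0.2% | 1.7% |
| 0.8 | 1.6 vs 0.8 | 0.2% | 1.5% |

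The reason is simple. With five discordant pairs all in one direction, exact McNemar gives p = 2 × 0.5⁵ = 0.063; with six, 2 × 0.5⁶ = 0.031. At least six are needed, and the expected excess is under one person.

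**Chance abnormalities.** With 0.8 to 1.2 expected on placebo, the probability of at least one is about 1 − (1 − 0.8/28)²⁸ = 0.56 to 1 − (1 − 1.2/28)²⁸ = 0.71 for one marker.

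**Larger shifts.** Power of the combined count is about 9% to 14% at 0.75 SD, 34% to 44% at 1 SD and 92% to 97% at 1.5 SD. The paired test has at least 97% at all three.

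**The case against.** The strongest reply is that 3.4 sets a threshold for reportable individual events and names no test, so the low power belongs to an analysis nobody planned. That is fair. McNemar is an assumption used to show how little the count can say; the documented gap is that no between-treatment summary is specified.

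A reader might infer that the endpoint has almost no chance of detecting any drug effect. The working does not support that: the combined count is weak only for modest shifts and would catch a large one. The documents also do not establish that a 0.5 SD change within the range matters for bleeding.

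A reader might also infer that the protocol calls bleeding the main risk of this product. It does not. Section 1.3 says so of vitamin E supplements in general and reports no such signal for gamma tocopherol.

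Nor are participants left unmonitored. Bleeding events are a separate endpoint (3.4), coagulopathy is graded (7.1.2), bruising or bleeding is scored (5.2.8) and queried during dosing, and extra tests may be done for abnormal bruising (7.3.1).

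The wording in 3.4 gives no direction, so low values could count. But it requires a significant change, so a trivially low value need not be an event. This point supports only separate tabulation.

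Finally, the PT/aPTT exclusion item (the second item lettered g under criterion 1 of 4.2) also covers the treatment period. A participant with an abnormal period 1 value might therefore have no period 2 value, and an analysis restricted to complete pairs could lose the most affected people. This stands, and the fix has to handle it.

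**Conclusion.** The point holds in a limited form. The structure is documented: a range-only endpoint, normal values required at entry, one value per treatment for each completer, and no planned comparison of them. For a modest shift of about 0.5 SD, the paired values are far more informative than the count under every correlation examined. The advantage in power shrinks as the shift grows and is small by 1.5 SD.

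The power figures depend on the assumed range, correlations and test, because the documents supply no SD, limits or expected shift for PT or aPTT. The case for the change does not depend on their exact values, since an estimate with an interval is available from blood already being drawn. This is an improvement to safety reporting. It does not call the primary result or the individual safety rules into question.

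**What to change.** In 3.4 and 6.2, add that PT, aPTT and INR will be analysed as continuous values. Report the within-participant gamma tocopherol minus placebo difference (V3 versus V6) with a 95% CI, from a crossover mixed model with treatment and period as fixed effects and participant as a random effect. V0 is available as a common baseline; there is no separate period 2 baseline.

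State that all available values enter the model, so that a participant who stops after an abnormal period 1 value still contributes, and report how many such participants there are.

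Keep the out-of-range listing and the individual safety rules as they are. Tabulate values above and below the range separately, by treatment.

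The cost is SAP wording and one table, with no new blood draw or visit.
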